Medication will be dispensed on Monday through Friday during working pharmacy hours. Participants will receive both pens at time of drug teaching and first dose administration. Participants will be monitored for approximately 15-20 minutes after their first injection. Teaching will be performed by designated nurses from the study team in either the inpatient setting or endocrinology clinic, for patients and their caregivers, if applicable.

Administration – Describe acceptable routes and methods of administration and any associated risks of administration.

Recommended dose is 80 mcg subcutaneously once daily. There is a small risk of minimal bleeding. Advised to administer initially where the patient can sit or lie down in case symptoms of orthostatic hypotension occur. Administration of the first dose will be performed in person with a designated nurse from the study team.

Toxicity – Accurate but concise listings of major toxicities. Rare toxicities, which may be severe, should be included by indicated incidence. Also adverse interactions with other drugs used in the protocol regimen as well as specific foods should be noted. Address significant drug or drug/food interactions in the consent form as well. List all with above details.

Orthostatic Hypotension

Orthostatic hypotension may occur with TYMLOS (abaloparatide), typically within 4 hours of injection. Associated symptoms may include dizziness, palpitations, tachycardia or nausea, and may resolve by having the patient lie down. For the first several doses, TYMLOS (abaloparatide) should be administered where the patient can sit or lie down if necessary

Hypercalcemia

TYMLOS (abaloparatide) may cause hypercalcemia. TYMLOS (abaloparatide) is not recommended in patients with preexisting hypercalcemia or in patients who have an underlying hypercalcemic disorder, such as primary hyperparathyroidism, because of the possibility of exacerbating hypercalcemia. Patients will be screened by our endocrinologist who will review calcium levels and underlying hypercalcemic disorders. Patients with persistent hypercalcemia or hypercalcemia refractory to treatment, will be identified by our endocrinologist, and if appropriate, these patients will be excluded at the discretion of the endocrinologist.

Hypercalciuria and Urolithiasis

TYMLOS may cause hypercalciuria. It is unknown whether TYMLOS may exacerbate urolithiasis in patients with active or a history of urolithiasis. If active urolithiasis or pre-existing hypercalciuria is suspected, measurement of urinary calcium excretion should be considered. Patients will be screened by our endocrinologist who will review urine and serum calcium levels and active or recurrent urolithiasis. Patients with hypercalciuria or urolithiasis, if appropriate, will be excluded at the discretion of the endocrinologist.

Risk of Osteosarcoma

Abaloparatide caused a dose-dependent increase in the incidence of osteosarcoma in male and female rats after subcutaneous administration at exposures 4 to 28 times the human exposure at the clinical dose of 80 mcg. It is unknown whether TYMLOS will cause osteosarcoma in humans. The use of TYMLOS is not recommended in patients at increased risk of osteosarcoma including those with Paget's disease of bone or unexplained elevations of alkaline phosphatase, open epiphyses, bone metastases or skeletal malignancies, hereditary disorders predisposing to osteosarcoma, or prior external beam or implant radiation therapy involving the skeleton. Cumulative use of TYMLOS and parathyroid hormone analogs (e.g., teriparatide) for more than 2 years during a patient's lifetime is not recommended. In our study, we are excluding anyone who has had any exposure to these anabolic medications in the past. Our duration of treatment is only 8 weeks (instead of the 2-year recommendation by the company) which further minimizes this risk.

Toxicity

In toxicity studies in rats and monkeys of up to 26-week and 39-week duration, respectively, findings included vasodilation, increases in serum calcium, decreases in serum phosphorus, and soft tissue mineralization at doses greater than or equal to 10 mcg/kg/day. The 10 mcg/kg/day dose resulted in systemic exposures to abaloparatide in rats and monkeys that were 2 and 3 times, respectively, the exposure in humans at daily subcutaneous doses of 80 mcg.

Is it FDA approved: (include FDA IND Number)

1. in the dosage form specified? If no, provide justification for proposed use and source of the study drug in that form.

Yes PIND 146326, NDA 208743

2. for the route of administration specified? If no, provide justification for route and describe the method to accomplish.

Yes

3. for the intended action?

No. However, the proposal involves use as an experimental treatment of a fracture that is most common in elderly patients with osteoporosis, and the study drug is approved for the treatment of individuals with osteoporosis who are at high risk for these fractures.

SUBJECT CHARACTERISTICS, IDENTIFICATION AND RECRUITMENT

Subject Selection: Provide rationale for subject selection in terms of the scientific objectives and proposed study design.

The study population includes patients greater than or equal to the age of 50. This is the population that sustains dens fractures most frequently.

Vulnerable Populations: Explain the rationale for involvement of subjects (e.g., cognitively impaired, Non-English speaking, prisoners, students). Discuss what procedures or practices will be used in the protocol to minimize their susceptibility to undue influences and unnecessary risk (physical, psychological, etc.).

Not applicable

Inclusion/Exclusion Criteria: Eligibility and ineligibility criteria should be specific. Describe how eligibility will be determined and by whom. Changes to the eligibility criteria at a later phase of the research have the potential to invalidate the research.

Treatment Subjects

Inclusion Criteria (all must be yes)

1. Age 50 years or older at time of consent
2. Anderson and D'Alonzo type II dens fracture identified on cervical spine CT, with or without a C1 ring injury. Type II dens fractures are defined as involving the area of the dens between the inferior aspect of the anterior C1 ring and not extending into the superior articular facets of C2.
3. Fracture is deemed amenable to non-operative treatment by treating fellowship trained spine surgeon
4. Fracture occurred within the 3 weeks before consent
5. Report of ≥ 12 months of amenorrhea within the last year if the patient is female

Exclusion Criteria (all must be no)

6. Personal history of radiation therapy to the skeleton
7. Personal history of osteosarcoma
8. Personal history of Paget's disease
9. Personal history of bone metastases or skeletal malignancy
10. Hereditary disorders predisposing to osteosarcoma
11. Prior teriparatide or abaloperatide use
12. Use of denosumab within the past year
13. Psychological impairment that precludes following hard collar immobilization recommendations
14. Ineligible based on history of active or recurrent kidney stones, CMP, PTH, Phos results to be determined on a case-by-case basis by an endocrinologist on the study team

Historical Comparison Subjects

Inclusion Criteria (all must be yes)

1. Age 50 years or older at time of fracture
2. Anderson and D'Alonzo type II dens fracture identified on cervical spine CT, with or without a C1 ring injury. Type II dens fractures are defined as involving the area of the dens between the inferior aspect of the anterior C1 ring and not extending into the superior articular facets of C2.
3. Fracture injury occurred within 10 years before consent
4. The patient completed 12 (+/- 1) weeks of hard collar immobilization

Exclusion Criteria (all must be no)

5. Any history of prior teriparatide or abaloperatide use
6. Use of denosumab in the past year

Inclusion of Minorities and Women: Describe efforts to include minorities and women. If either minorities or women are excluded, include a justification for the exclusion.

Women will be included in the study whenever the eligibility criteria are met. Every effort will be made to recruit minorities. Recruitment efforts will not differ by sex or by ethnicity.

Inclusion of Children: Describe efforts to include children. Inclusion is required unless a clear and compelling rationale shows that inclusion is inappropriate with respect to the health of the subjects or that inclusion is inappropriate for the purpose of the study. If children are included, the description of the plan should include a rationale for selecting or excluding a specific age range of children. When included, the plan must also describe the expertise of the investigative team in working with children, the appropriateness of the available facilities to accommodate children, and the inclusion of a sufficient number of children to contribute to a meaningful analysis relative to the purpose of the study. Provide target accrual for this population. Identify whether children are wards of the state. **If children are excluded** then provide appropriate justification.

The fracture of interest occurs very rarely in minor subjects, and the safety and effectiveness of the study drug has not been established in pediatric patients. Children will not be included in this study.

For protocols including the use of an investigational drug, indicate whether women of childbearing potential have been included and, if not, include appropriate justification.

The study drug is not indicated for use in females of reproductive potential and the safety of the study drug in pregnant women is unknown. We are therefore limiting recruitment to that of older adults (\geq age 50). Women of childbearing potential will not be included in this study.

If HIV testing is included specifically for research purposes explain how the test results will be protected against unauthorized disclosure. Include if the subjects are to be informed of the test results. If yes, include the process and provision for counseling. If no, a rationale for not informing the subjects should be included.

Not applicable

Will the SONA psychology Pool be utilized? *Include documentation indicating permission to use this recruiting tool* Yes No

FINANCIAL CONSIDERATIONS

Describe all potential research related expenses to subjects:

Any additional study process or test that is beyond the routine medical costs for non-operative management of dens fracture will be covered by the study; such research-driven procedures are indicated in Tables 1 and 2 above for each of the treatment and control groups, respectively. No additional cost will be charged to the treatment subjects for participating in the study, other than travel to clinic if needed.

Compensation for participation: Describe all plans to pay subjects, either in cash, a gift or gift certificate. Please note that all payments must be prorated throughout the life of the study. The IRB will not approve a study where there is only a lump sum payment at the end of the study because this can be considered coercive. The amount of payment must be justified. Clarify if subjects will be reimbursed for travel or other expenses.

Not applicable

The active control subjects (Control cohort A) will be compensated \$50 via mail after research clinic visit, in compensation for their travel and time in returning to clinic for research procedures.

Collaborating Institutions

Will this research be conducted in collaboration with other sites at other locations?

Yes No

If so, complete the following for all collaborating institutions:

Institution Name	Describe Involvement	Is there an IRB? If yes, attach approval or explanation	Are other permissions required? If yes, attach approval or explanation

INFORMED CONSENT

a. Type of Consent

i. Are you obtaining Written Consent?

	Yes		No
	Yes		No

If yes, will there be more than one consent document?

If yes, how many consent documents and for what populations.

Two written informed consent forms will be used; one for the treatment subjects and one for the historical comparison subjects. Two consent forms will be used because the study procedures and associated risks for the treatment subjects are different from those for the comparison subjects.

ii. Are you requesting a Waiver of Informed Consent?

	Yes		No
--------------------------	-----	-------------------------------------	----

This request means that you will not be obtaining verbal nor written consent. If yes, complete the form Request for a Waiver of Informed Consent/Authorization/Documentation in UVMClick.

iii. Are you requesting an Alteration of Informed Consent Procedures?

	Yes		No
--------------------------	-----	-------------------------------------	----

This is a request to alter an individual's informed consent or elements of informed consent. Deception in research would be one example when consent would be altered. See [Policies and Procedures Manual](#) for more information about when a subject's consent may be altered. If yes, complete the smart form Request for a Waiver of Informed Consent/ Authorization/ Documentation in UVMClick.

iv. Are you requesting a Waiver of Documentation of Informed Consent?

	Yes		No
--------------------------	-----	--------------------------	----

This request means you are obtaining verbal or implied consent without obtaining the subject's signature on a consent form. See manual for the criteria required to obtain this type of waiver.

If yes, complete the form Request for a Waiver of Informed Consent/Authorization/Documentation in UVMClick.

v. Do you intend to obtain consent from a legally authorized representative?

If yes, describe the process.

	Yes		No
--------------------------	-----	-------------------------------------	----

vi. Are you requesting a short form consent process for non-English speaking subjects? Yes NoIf yes, please describe. Guidance available in the [Policies and Procedures Manual](#).

--

b. Consent Process

i. Once a prospective subject is identified, who initiates the informed consent discussion and answers questions presented by the subject or the subject's family?

Designated key personnel of the study will be able to initiate the informed consent discussion and answer questions presented by the subject or the subject's family.

ii. Where (in what setting) is the informed consent process initiated? How much time is the subject given to decide?

For the treatment subjects, ideally the informed consent process will be initiated in the hospital setting within a

day or two after the diagnosis. If the patient is diagnosed at an outside facility and presents to the outpatient spine clinic for follow up, the informed consent process would be initiated there.

For potential control subjects who are living at time of identification and have not previously had a cervical CT under routine care after completion of hard collar treatment; the informed consent process will be initiated either in person or via letter or email from [name]. Designated research personnel will follow-up in person or by phone within two weeks to inquire about interest in study participation. The same, approved recruitment phone script will be used whether it is in person or by phone.

- For participants interested in active study participation (*control cohort A*), written informed consent will be obtained in person at UVMMC in a private room, prior to study imaging or administration of the study questionnaires.
- For eligible control subjects who indicate at time of recruitment phone call that they are not interested in active study participation, the patient will be invited to verbally consent to participation in *control cohort B*. A verbal consent script has been developed for this purpose.

Potential control subjects who are living at time of identification and have previously had a cervical CT under routine care after completion of hard collar treatment will be approached using the approved verbal consent script described above. The verbal consent script offers the opportunity for (passive) participation in *control cohort B* and introduces the researcher as a member of [name] research team.

In all cases, subjects will be given as much time as they need to discuss the study with others and make their decision. However, treatment patients and comparison subjects will need to be enrolled within 3 weeks of fracture injury and 10 years of fracture injury, respectively, to be eligible for study participation (see Inclusion and Exclusion Criteria, above).

iii. Is the principal investigator present for the initial and subsequent informed consent discussions with the subject?

Either the PI or other designated key study personnel will be present for the initial and subsequent consent discussions with the subject.

iv. What other method of documentation is used to record the informed consent process, in addition to the executed consent form? See an [example of documentation](#) of the informed consent **process** under consent templates on our forms page.

Written informed consent processes will be documented using an Informed Consent Process Documentation form. This form is based on the standard IRB template and will be filed together with the informed consent form in the study folder for each consented subject.

Verbal consent processes will be documented using an Informed Consent Process Documentation form. This form will be maintained together with a record of the verbal consent script used for that subject.

Information Withheld From Subjects: Will any information about the research purpose and design be withheld from potential or participating subjects? If so, explain and justify the non-disclosure and describe plans for post-study debriefing.

Not applicable

Research Data Management Plan: The Research Data Management and Security Plan form must be completed. The form, along with guidance, can be found in our [forms library](#) and must be submitted with your initial application.

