Eligible patients will receive standard treatment of 12(+/-1) weeks of rigid hard collar immobilization, as well as an 8-week course of PTH analog during this time. Drug will be initiated as soon after the injury as possible, and at the latest 4 weeks from injury which will allow for completion of 8 weeks of drug administration during the period of hard collar immobilization. Teaching on drug administration will be provided for enrolled patients and their caregiver, if applicable, by designated study personnel prior to drug initiation – either while inpatient, or at the outpatient endocrinology clinic visit. Treatment subjects will otherwise receive the routine care that was provided to historical controls in terms of length of hard collar immobilization spine fracture clinic follow-up and radiographic evaluation. Treatment subjects will be followed with weekly phone calls (see Table 1) by clinical personnel on the study team for the duration of the 8-week treatment.

Study participants will be followed at the spine fracture clinic according to our usual protocol every 4 weeks +/- 1 week (from the date of injury) out to 12 weeks. All patients will fill out VAS Neck and Neck Disability Index (NDI) physical function questionnaires at each clinic visit. Use of narcotic pain medication will be collected at each clinic visit under routine care.

DEXA scans will be obtained for all participants to assess baseline bone density. If a patient has had a DEXA scan for routine care within the 12 months prior to consent, that scan will be used as the baseline test and a separate test for research will not be ordered. If needed, baseline DEXA will need to be completed after consent and by time of the 12 week visit.

All radiographs for treatment subjects will be obtained as part of routine care. These include AP/Lateral at each of the 4 (+/-1) week and 8 (+/-1) week clinic visits, and Flex/Ext at the 12 (+/-1) week clinic visits. Final (12 +/-1 week) flexion/extension radiographs will be evaluated for translational motion at the fracture site measured at the posterior cortex of the dens and evaluated by the following criteria: None, Minimal (<2 mm), Moderate (2-4 mm), Mobile (>4 mm).

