Visit Time point	Screening and baseline procedures	4-week visit (within 4 weeks of fracture)	8-week visit (8 +/- 1 weeks after fracture)	12-week visit (12 +/- 1 weeks after fracture)
Informed consent	X*			
Spine Fracture Clinic visit	X (if needed for routine care)	X	X	X
Physical Exam	X	X	X	X
Neck Disability Index		X	X	X
VAS Neck		X	X	X
(Eligibility confirmed by study team after screening labs completed and before study drug administration)				
Endocrinology Clinic visit (only if the patient is not recruited while inpatient)	X*			
Study drug teaching and first dose of Tymlos	X*			
Tymlos self-administration	X* (daily for 8 weeks after drug teaching)			
CMP	X*			
PTH	X*			
Phos	X*			
HbA1c	X*			
AP/Lateral XR	X	X	X	(X if required for routine care)
Flex/Ext XR				X
CT Cervical	X			X*
DEXA	X** (by time of 12-week visit)			
Phone check-in	X* (each week +/- 2 d after first dose for the 8-week treatment period)			

* These procedures are research-driven and deviate from routine care of treatment patients in clinic.

** The DEXA scan is completed for research purposes only if not previously completed within 12 months before consent for routine care purposes.

Spine fracture clinic (and endocrinology visit, for patients not recruited in the inpatient setting) involve medical history under routine care.

Neck Disability Index and VAS Neck physical function are questionnaires given to patients during the clinic visit and prior to medical evaluation. These take less than 10 minutes to fill out, they are validated, and they are standard/routine in many clinic visits. These questionnaires will provide secondary outcome measures.

The study drug (abaloparatide) is an FDA approved medication used to treat osteoporosis. It is a daily subcutaneous injection administered by the patient. This requires patient education.

CMP, PTH, Phos, and HbA1c are laboratory tests performed by venipuncture. Blood work includes complete metabolic profile, phosphorous, parathyroid hormone, and hemoglobin A1c. Many of these patients have osteoporosis at baseline and these tests allow us to screen, quantify, and subsequently manage their osteoporosis. This blood work is standard of care for evaluation and treatment of osteoporosis. In this study, CMP, PTH and Phos will be obtained as screening labs (see Screening Procedures, below). HbA1c

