levels are meant for baseline data collection as they relate to the ability to heal fractures, and are tested with screening labs to prevent need for additional blood draws for research purposes.

AP/Lateral XR and Flex/Ext XR is a standard set of X-rays of the cervical spine used to evaluate the secondary outcome of translational motion at the fracture.

CT Cervical spine is for research purposes at the 12-week mark only. This will be used to measure fracture union rate (the primary outcome).

The DEXA scan is a low dose x-ray scan used as a screening tool recommended for all women over the age of 65. The radiation is so low (significantly lower than a chest x-ray) that this machine and radiation is not formally regulated in the United States. Many of these patients have osteoporosis at baseline and this test allows us to screen, quantify, and subsequently manage their osteoporosis. *In this study*, DEXA scans will be obtained to evaluate bone health as it relates to the ability to heal a fracture. If a patient's T-score is ≤ -2.5 at the spine or hip in a DEXA scan obtained for research purposes, the study team will notify the patient of the finding and refer her/him for follow-up care, as appropriate.

Procedures for control cohort A (active control participants)

Table 2. Research procedures for control patients who provide written consent to active study participation (control cohort A).

Item	UVMMC	Via Mail
Informed consent	X	
Neck Disability Index	X	
VAS Neck	X	
Cervical CT Scan	X	
Flexion-extension cervical x-ray	X**	
Compensation		X*

* After completion of CT scan

** The XR is only obtained for research purposes if a flexion-extension cervical x-ray was not obtained 11 or more weeks after initiation of hard collar treatment as part of their routine care.

Procedures for control cohort B (review-only control participants)

Control cohort B includes subjects who

- (a) Previously had a cervical CT scan obtained after completion of their hard collar treatment under routine care; or
- (b) do not provide written consent to active study participation but provide verbal consent to allow the study team to collect existing information that is available from their treatment in the electronic medical record; or
- (b) are deceased and are not available for informed consent

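### The DEXA labelled baseline may be taken as late as the 12-week visit, after 7 to 8 weeks of study drug, so some values may not be baseline values

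*Combined protocol and SAP*

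**What the plan says.** Under Study Design, Treatment subjects, the protocol states the purpose of the scan: "DEXA scans will be obtained for all participants to assess baseline bone density". An existing scan is accepted under one condition: "If a patient has had a DEXA scan for routine care within the 12 months prior to consent". Otherwise a research scan is ordered, and "baseline DEXA will need to be completed after consent and by time of the 12 week visit". Table 1 lists the DEXA under screening and baseline procedures but repeats the 12-week limit. Neither place ties the scan to the first dose.

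The same section sets the start of treatment: "Drug will be initiated as soon after the injury as possible, and at the latest 4 weeks from injury". Table 1 gives the duration as "daily for 8 weeks after drug teaching" and places the 12-week visit at 12 weeks after fracture, plus or minus 1.

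The text after Table 1 explains why the scan is done: "DEXA scans will be obtained to evaluate bone health as it relates to the ability to heal a fracture". It adds that a patient whose research scan shows a T-score of -2.5 or lower at the spine or hip is told and referred for follow-up.

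Statistical Considerations plans a multivariable regression. It names no covariates and does not list bone density as an outcome.

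**The concern.** A baseline measurement describes the patient before treatment. Here the rule lets the measurement follow the treatment, and the treatment is a drug that the protocol describes as approved for osteoporosis. Under Potential Benefit it says that the drug might serve as early osteoporosis treatment in these subjects, so the plan itself expects the drug to act on bone.

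Two uses of the scan are at stake. The first is its stated purpose of relating bone health to healing. If some treated patients contribute pre-drug values and others post-drug values under one label, the relation is blurred. The second is the T-score reported to the patient, which after a late scan may not reflect pre-drug status.

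The protocol's handling of HbA1c makes the contrast plain. HbA1c is also collected for its bearing on fracture healing, but it is drawn with the screening labs and so before dosing. The stated reason is to spare a second blood draw. The result is still a true baseline value, which the DEXA rule does not secure.

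**Working it through.** The plan states no figure on this point, so there is none to reproduce. The check is one of timing.

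**Inputs**
- Drug start *s*: week 0 to week 4 after injury (Study Design sets the latest start at week 4; week 0 is the earliest conceivable).
- Duration: 8 weeks (Study Design and Table 1).
- Visit that closes the DEXA window, *v*: weeks 11 to 13 after fracture (Table 1).
- Planned treated patients: 10 (Statistical Considerations).

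**Formulas**
- Weeks of drug before a scan at visit *v*: min(8, *v* − *s*).
- Weeks since the course ended: max(0, *v* − *s* − 8).

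**Results for a scan at the permitted limit, full course taken** (weeks of drug received / weeks since the course ended)

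| Drug start | Visit week 11 | Visit week 12 | Visit week 13 |
|---|---|---|---|
| Week 0 | 8 / 3 | 8 / 4 | 8 / 5 |
| Week 1 | 8 / 2 | 8 / 3 | 8 / 4 |
| Week 2 | 8 / 1 | 8 / 2 | 8 / 3 |
| Week 3 | 8 / 0 | 8 / 1 | 8 / 2 |
| Week 4 | 7 / 0 | 8 / 0 | 8 / 1 |

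In 14 of the 15 combinations the scan follows the whole course. In the other (start at week 4, visit at week 11) it follows 7 of 8 weeks. No combination gives a pre-drug value. Even with the latest start and the earliest visit, the last 11 − 4 = 7 weeks of the permitted window lie after the first dose.

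**Who is affected.** Only treated patients with no routine scan in the 12 months before consent whose research scan is then done after dosing begins. The documents do not give that share. With 10 treated patients, each such scan is 1/10 = 10% of the arm.

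**Does it reach the between-group comparison?** Table 2 (control cohort A) contains no DEXA, and the information to be collected for control cohort B does not mention it. The statement that all participants are scanned stands under the Treatment subjects heading, so it is not a clear promise of control scans. As written, bone density can be related to healing only within the treated group.

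**The case against.** The strongest reply is that little depends on this scan. Bone density is neither an outcome nor a named covariate, and the stated purpose fits a purely descriptive use. The study is a pilot, and any analysis of bone density would be exploratory in about 10 patients. Patients with a recent routine scan contribute a pre-drug value in any case. Many patients are inpatients with an acute fracture and dosing is to begin promptly, so a generous window is practical. All of this stands, and it limits the consequence. It does not rescue the label, because a scan after 7 or 8 weeks of drug is not baseline even in a descriptive table.

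A reader might infer more than the documents support, in three ways.
- **That a post-drug bone-density covariate would absorb part of the drug effect in the primary analysis.** This would need bone density in a model comparing treated patients with controls. No such covariate is named and controls have no planned DEXA. Within the treated group everyone receives drug, and partial-course patients are described separately.
- **That a given percentage of patients would be moved across the -2.5 line.** Any such figure would need an assumed 8-week T-score rise, an assumed T-score distribution and an assumed share scanned late. The documents supply none of these.
- **That routine scans up to 12 months old are part of the same fault.** They may be dated, but they precede the study drug.

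**Conclusion.** The point holds in a limited form. The text and Table 1 agree on a rule under which a scan called baseline can follow 7 to 8 weeks of an osteoporosis drug. This weakens the scan's stated purpose within the roughly 10 treated patients, and it means that a reported T-score may not describe the patient before treatment. The primary CT comparison is not affected as written.

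The timing result rests only on the protocol's own windows and on the patient taking the full course. The size of any distortion cannot be computed, because the documents give neither the density change over 8 weeks of drug nor the share of patients who need a research scan. The change is still worth making before enrolment, because a pre-dose scan that was not taken cannot be recovered later.

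**What to change.** - Keep the rule that accepts a routine scan from the 12 months before consent, and record its date.
- For patients who need a research scan, schedule it before the first dose or within a short window after it whose length the protocol states. Fourteen days is one possible choice; the documents give no basis for an exact figure. The scan should not change when dosing starts.
- Record the scan date and the number of doses received before it. Flag scans outside the window as on-treatment, and do not report or model them as baseline.
- Make the same change in Table 1.
- If bone density is to be compared or adjusted for between groups, extract any routine DEXA done near the fracture from control charts and say so in the plan.

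**Cost.** The scan is already planned, so the change is one of scheduling plus a few data fields, with some chart review if control values are wanted. The downside is that some patients may miss the early window and have no baseline value. Their number should be reported.
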